### **5.5.2 Dispensing the study treatment**

Each study site will be supplied by Novartis with study drug in packaging of identical appearance.

The study drug packaging has a 2-part label. A unique medication number is printed on each part of this label. Investigator staff will identify the study drug package(s) to dispense to the patient by contacting the IRT system and obtaining the medication number(s). Immediately before dispensing the package to the patient, investigator staff will detach the tear-off portion of the label from the packaging and affix it to the source document (Drug Label Form) for that patient’s unique patient number and if applicable, logged in the IRT system drug accountability web-based portal.

[figure not shown]
### **5.5.3 Supply, storage and tracking of study treatment**

Study treatment must be received by a designated person at the study site, handled and stored safely and properly, and kept in a secured location to which only the investigator and designated assistants have access. Upon receipt, all study drugs should be stored according to the storage instructions specified on the drug labels. Should a storage excursion occur, the site must contact Novartis to determine if the study medication can continue to be used. Clinical supplies are to be dispensed only in accordance with the protocol.

Medication labels will be in the local language and comply with the legal requirements of each country. They will include storage conditions for the drug, but no information about the patient except for the medication number.

The investigator must maintain an accurate record of the shipment and dispensing of study drug in a drug accountability ledger. Monitoring of drug accountability will be performed by the field monitor during site visits and at the completion of the trial. Patients will be asked to return all unused study drug and packaging at each visit, and at the end of the study, or at the time of study drug discontinuation.

At the conclusion of the study, and as appropriate during the course of the study, the investigator will return all used and unused study drug, packaging, drug labels, and a copy of the completed drug accountability ledger to the Novartis monitor or to the Novartis address provided in the investigator folder at each site.

#### **5.5.4 Instructions for prescribing and taking study treatment**

Study medication will be dispensed at the Baseline visit and each subsequent treatment visit thereafter as per the schedule of assessments. The patients will receive up to 6 bottles of oral medication containing 35 capsules per bottle at each visit, which will provide enough medication through their next regularly scheduled visit.

The investigator should promote compliance by instructing the patient to take the study drug exactly as prescribed and by stating that compliance is necessary for the patient's safety and the validity of the study. The patient should be instructed to contact the investigator if he/she is unable for any reason to take the study drug as prescribed. Instruction should also be given to the patient to open and use one bottle at a time. All unused medication as well as empty bottles should be returned to the investigator at the next regularly scheduled visit.

Study medication should be taken once a day, preferably at the same time every day, with or without food.

Once the eligibility of a patient for entry into the study has been confirmed based on the study inclusion/exclusion criteria, study medication will be dispensed via the IRT system (see [Section 5.5.2](#)).

Patients enrolling directly from a blinded study in which a blinded comparator arm exists (placebo or active comparator) may require blinded first dose observation, performed by a blinded first-dose administrator who cannot discuss the findings with the patients or anyone else associated with the clinical trial unless this is required for a medical reason.

[figure not shown]
If patients transition into this extension study from the comparator arm of an open-label controlled study, the first dose of the study drug (capsules) administered at the Baseline visit in this study must be administered in the clinic under the supervision of the investigator or designee, or in accordance with the local label.

Similarly, any patient who re-initiates fingolimod treatment after an interruption, the first dose of the study drug (capsules) administered at treatment re-initiation must be administered in the clinic under the supervision of the investigator or designee, or in accordance with the local label if the following circumstances apply:

- The treatment lasted for 14 days or less and was interrupted for 1 day or more, or
- The treatment lasted for more than 14 days and less than 29 days and was interrupted for more than 7 consecutive days, or
- The treatment lasted for 4 weeks or more and was interrupted for more than 14 consecutive days.

Advice from a cardiologist should be sought and overnight monitoring with continuous ECG is required under the following circumstances:

- The pre-dose ECG shows a QTc interval >470 msec (females) or >450 msec (males) or a second degree or higher AV block
- The patient has relevant risk factors for QT prolongation, for example, hypokalaemia or hypomagnesemia, sick-sinus syndrome, or sino-atrial heart block

- The patient has known ischemic heart disease, history of myocardial infarction, congestive heart failure, history of cardiac arrest, cerebrovascular disease, uncontrolled hypertension or severe untreated sleep apnea period
- The patient has a history of recurrent syncope or symptomatic bradycardia
- The resting heart rate pre-dose is <45

For patients receiving (at treatment re-initiation) beta blockers, heart-rate slowing calcium channel blockers (e.g. ivadabine, verapamil, or diltiazem), or other substances which may decrease heart rate such as digoxin, anticholinesteratic agents or pilocarpine, advice from a cardiologist should be sought regarding the switch to non-heart-rate lowering medicinal products prior to re-initiating treatment. If a switch to non-heart rate lowering drugs is not possible, patients have to be observed overnight.

Patients transferring from blinded placebo-controlled or active comparator trials, or patients enrolling into the study who have been off fingolimod treatment for 90 days or more will need additional visits at 1 and 3 months post-first dose (see [Table 6-1](#) and [6-2](#)).

Patients requiring first dose monitoring should receive the first dose of study drug at the study center at a time which will allow for the required 6-hour post-dose monitoring to occur as well as to allow for additional time for extended monitoring, if necessary. The patient will stay at the study center for a minimum of 6 hours to monitor for signs and symptoms of bradycardia. All patients will have an ECG performed prior to dosing and at the end of the 6-hour monitoring period. Sitting heart rate and blood pressure will also be monitored before the first dose of fingolimod and every hour for at least six-hours thereafter. The patient may be discharged if specific discharge criteria (outlined in [Appendix 4](#)) are met. Hourly monitoring will be extended until findings have resolved if the discharge criteria are not met and should pharmacologic intervention be required during first-dose observation, overnight monitoring in a medical facility should be instituted and the first-dose monitoring procedures should be repeated upon the 2nd dose (see [Appendix 4](#) for Guidance for monitoring of patients taking their first dose of the study drug).

[figure not shown]
All medication prescribed and dispensed to the patient and all dose interruptions during the study must be recorded on the Dosage Administration Record eCRF.

All drug kits assigned by the IRT system will be recorded in the IRT system.

### **5.5.5 Permitted dose adjustments and interruptions of study treatment**

Study drug dose adjustments are not permitted, although interruptions may be warranted based on safety monitoring guidelines and should be recorded on the Dosage Administration Record eCRF.

Absolute lymphocyte count  $<0.2 \times 10^9/l$ , if confirmed, should lead to treatment interruption until recovery. (See [Appendix 5](#) for safety monitoring guidelines). Should the patient interrupt study drug, and the Investigator decide to re-initiate treatment with study drug, the first-dose monitoring procedure may be required for the restart of study drug (see [Appendix 4](#) for details).

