### **5.5.9 Discontinuation of study treatment and premature patient withdrawal**

Patients may voluntarily withdraw from the study for any reason at any time. They may be considered withdrawn if they state an intention to withdraw, fail to return for visits, or become lost to follow-up for any other reason.

When a patient withdraws from Study Part One and does not continue on fingolimod, either in a study or non-study setting, they must return for two Follow-up visits, 3 months and 6 months after stopping study drug.

When a patient withdraws from Study Part Two, and does not continue on fingolimod, either in a study or non-study setting, they must return for one Follow-up visit, 3 months after stopping study drug.

If premature withdrawal occurs for any reason, the investigator must make every effort to determine the primary reason for a patient's premature withdrawal from the study and record this information on the appropriate eCRF.

Study drug must be discontinued for a given patient if the investigator determines that continuing it would result in a significant risk for that patient. In addition, study drug must be discontinued based on results of safety monitoring as outlined in [Appendix 5: Guidance on safety monitoring](#) and [Appendix 7: Guidance for Ophthalmic Monitoring](#). The following conditions/events may be considered sufficient to support a decision about the study drug discontinuation in individual cases:

- serious adverse event (e.g. cardiac failure, diagnosed malignancy, new neurological symptoms accompanied by MRI findings unexpected for MS) abnormal laboratory value(s) or abnormal test result(s) (e.g. ophthalmic findings).
- withdrawal of consent
- pregnancy (please see [Section 6.5.8](#) and [Section 7.3](#))
- use of prohibited medications, listed in [Section 4.2](#) and [Section 5.5.8](#).
- adverse events
- protocol deviation
- unsatisfactory therapeutic effect
- patient's condition no longer requires study treatment
- administrative problems (e.g. patient's non-compliance)
- discontinuation warranted as per local label requirements

In addition to scheduled visits, patients who discontinue study drug due to adverse events or abnormalities on safety monitoring tests must be followed up with additional visits as needed in order to confirm the resolution of abnormalities.

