## 6.5.4 Laboratory evaluations

Screening laboratory tests and routine blood samples as described in [Table 6-1](#) will be collected and analyzed by the central lab during Study Part One. During Study Part Two, laboratory tests will be collected and analyzed by the study site (i.e., locally, not using a central lab).

For Study Part One, details regarding collection of samples, shipment of samples, reporting of results, lab normal ranges and alerting abnormal values will be supplied to the site before site initiation in a study laboratory manual. The results of the analysis will be made available to each site by the central lab at the earliest 48 hours after receipt of the samples by the central lab. Extreme values, specified in the "Criteria for clinically notable laboratory values and vital signs" are further specified in [Appendix 1](#), which will generate a "phone alert" to the investigator.

For Study Part Two, samples will be collected and reported in accordance with local laboratory policies. Lab results will not be recorded in the eCRF, but will remain as source documentation for ongoing safety assessment.

Investigators will be asked to comment on any abnormalities on the respective lab result page, including a notation of the clinical significance of each abnormal finding in the patient's source documents. The laboratory sheets will be filed with the patient source documents.

Abnormal laboratory values or test results should be recorded as adverse events only if they induce clinical signs or symptoms, are considered clinically significant or require therapy. Abnormal laboratory values alone should not be recorded on the adverse event eCRF; however, any diagnoses (or signs or symptoms, if a diagnosis is not possible) associated with the abnormal findings should be recorded on the adverse event eCRF.

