### **11.1 Protocol Amendments**

Any change or addition to the protocol can only be made in a written protocol amendment that must be approved by Novartis, Health Authorities where required, and the IRB/IEC. Only amendments that are required for patient safety may be implemented prior to IRB/IEC approval. Notwithstanding the need for approval of formal protocol amendments, the investigator is expected to take any immediate action required for the safety of any patient included in this study, even if this action represents a deviation from the protocol. In such cases, Novartis should be notified of this action and the IRB/IEC at the study site should be informed within 10 working days.

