## **Appendix 4: Guidance for Monitoring of patients taking their first dose of the study drug**

Initiation of fingolimod treatment results in a transient decrease in heart rate. After the first dose, the heart rate decrease starts within an hour and the Day 1 decline is maximal within 6 hours. With continued dosing, heart rate returns to baseline within one month of chronic treatment. In patients receiving fingolimod 0.5 mg this decrease in heart rate, as measured by pulse, averages approximately 8 beats per minute (bpm). Heart rates below 40 bpm were rarely observed. Patients who experienced bradycardia were generally asymptomatic but some patients experienced mild to moderate symptoms.

Initiation of fingolimod treatment has been associated with AV conduction delays, usually as first-degree atrio-ventricular blocks. Second-degree AV blocks, usually Mobitz type I (Wenckebach) have been observed in less than 0.5% of patients receiving Gilenya 0.5 mg in clinical trials. The conduction abnormalities typically were transient, asymptomatic, usually did not require treatment and resolved within the first 24-hours on treatment. Isolated cases of transient, spontaneously resolving complete AV block have been reported during post-marketing use of fingolimod 0.5 mg.

Therefore, guidance on the monitoring of patients taking their first dose or re-initiating treatment after interruption of treatment is provided.

The on-site first-dose administration monitoring is mandatory for the following patients:

- At the Baseline visit, in all patients enrolling into this trial from blinded controlled trials and patients from open-label controlled trials coming off the comparator arm.
- Patients who are off fingolimod treatment for the following durations:
- The treatment lasted for 14 days or less and was interrupted for 1 day or more, or
- The treatment lasted for more than 14 days and less than 29 days and was interrupted for more than 7 consecutive days, or
- The treatment lasted for 4 weeks or more and was interrupted for more than 14 consecutive days.

If applicable, the independent first-dose monitoring physician is responsible for monitoring following the 1st intake of the study drug and management of bradycardia symptoms should these occur. He/she must review vital signs during 6-hour monitoring, post-dose ECG and assess discharge criteria at 6 hours post-dose.

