### **Guidance on monitoring of patients with notable lymphopenia**

Fingolimod results in sequestration of a proportion of the circulating lymphocytes in lymph nodes with resultant reduction in circulating lymphocyte counts. Average circulating lymphocyte counts are expected to be around  $0.5-0.6 \times 10^9/L$  or  $500-600$  cells/ $\text{mm}^3$ . As such, the absolute total WBC, neutrophil and lymphocyte counts will be measured at each visit  $y$ . If the absolute lymphocyte count drops below  $0.2 \times 10^9/L$  or  $200$  cells/ $\text{mm}^3$  lymphocyte counts should be repeated regularly, at least monthly, and the patient should be reminded of the risk of infections and instructed to promptly report any symptoms of infections to the investigator. If monthly site visits create a logistical burden for the patient, local lymphocyte testing can be performed, with an eCRF comment added that lymphocyte counts were obtained locally and reviewed by the investigator. Study drug should be temporarily interrupted at the discretion of the investigator. Recovery of lymphocyte counts is expected to take approximately 1-2 months after stopping study drug given the long half-life of fingolimod. The patient should be evaluated and monitored for infections on a regular basis during this period.

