### **Guidance on monitoring of patients with infections**

All infections that develop during the study will be reported as AEs. Investigators are requested to specifically ask about infections at each visit. Treatment and additional evaluations will be performed at discretion of the investigator.

The investigator should be vigilant for risk of infections including opportunistic infections (with bacterial (e.g. atypical mycobacteria), viral (e.g. HSV, VZV, JCV), or fungal (e.g. cryptococcus agents), should remind the patient of the risk of infections, and instruct them to promptly report any symptoms of infections to the investigator. The patients must also be reminded to always carry their Patient Information Card (with site contact information and which identifies them as participants in a clinical study with an investigational agent with potential immunosuppressive effects) and to show this to any local healthcare provider they may consult and ask that the investigator be contacted.

When evaluating a patient with a suspected infection, the most sensitive tests available should be used (i.e. that directly detect the pathogen, as with PCR).

The investigator should consider early treatment with antimicrobial therapy on the basis of clinical diagnosis or suspicion thereof (e.g. antiviral treatment for herpes simplex or zoster) in consultation with infectious disease experts, as appropriate.

Investigators should be aware that in the post marketing setting with Gilenya, isolated cases of cryptococcal meningitis have been reported. Patients reporting symptoms and signs (such as,

but not limited to, headache accompanied with stiff neck, sensitivity to light, fever, confusion, tiredness, body aches, chills, vomiting, and/or nausea) consistent with meningitis should undergo prompt diagnostic evaluation. If cryptococcal meningitis is diagnosed, appropriate treatment should be initiated as soon as possible. The investigator should inform the Novartis medical expert of any such cases.

Investigators should consider the added immunosuppressive effects of corticosteroid therapy for treatment of MS attack/relapse and increase vigilance regarding infections during such therapy and in the weeks following administration.

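### Section 5.5.5 directs interruption for a confirmed lymphocyte count below 0.2 x 10^9/L, but Appendix 5, to which it refers, leaves interruption at that threshold to the investigator

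*Protocol*

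**What the plan says.** Section 5.5.5 (permitted dose adjustments and interruptions) sets the rule for lymphopenia. A count below 0.2 x 10^9/L, "if confirmed, should lead to treatment interruption until recovery". It then refers the site to Appendix 5 for the monitoring guidelines.

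The lymphopenia guidance in Appendix 5 starts from the same value, given as 0.2 x 10^9/L or 200 cells/mm3. It says that "lymphocyte counts should be repeated regularly, at least monthly, and the patient should be reminded of the risk of infections". On stopping the drug it says: "Study drug should be temporarily interrupted at the discretion of the investigator". It adds that counts are expected to recover about 1-2 months after stopping, and that the patient should be monitored for infection meanwhile.

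On where the counts are kept, Section 6.5.4 sends Part One samples to a central laboratory. In Part Two testing is local: "Lab results will not be recorded in the eCRF, but will remain as source documentation for ongoing safety assessment".

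**The concern.** Section 5.5.5 and Appendix 5 are both current protocol text and share one trigger, but they give different actions. One directs interruption until recovery once the value is confirmed. The other leaves temporary interruption to judgement and never mentions confirmation. A site that follows the cross-reference in Section 5.5.5 lands on the discretionary sentence.

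What is at stake is consistent safety conduct in a study whose primary objective is long-term safety and tolerability. Two sites with the same confirmed result could act differently, each relying on current text. Section 11 allows no authorized deviations, so a monitor working from Section 5.5.5 could also question a site that had followed Appendix 5.

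**Working it through.** No sample size, error rate or estimate is involved, so the check is a comparison of texts.

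**Same threshold.** One litre is 10^6 mm3, so 0.2 x 10^9/L = (0.2 x 10^9)/10^6 = 200 cells/mm3. Both texts, and the notable value in Appendix 1, use this number.

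| Element | Section 5.5.5 | Appendix 5, lymphopenia |
|---|---|---|
| Trigger | Below 0.2 x 10^9/L, confirmed | Below 0.2 x 10^9/L; confirmation not mentioned |
| Repeat counts | Implied by the need to confirm | At least monthly, as continuing monitoring; no action tied to a second low value |
| Interruption | Directed | Investigator's choice |
| Duration | Until recovery | Temporary; gives an expected recovery time only |
| Strength of wording | Should | Should, qualified by discretion |

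**The case that separates them.** Take a patient whose first count and repeat count are both below the threshold. Under Section 5.5.5 the drug should stop until recovery. Under Appendix 5 alone, continuing with at least monthly counts and counselling is compliant. Before confirmation the two texts do not conflict.

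**Whether another text decides it.** Appendix 1 lists the value as notable and gives no action. No order of precedence between Section 5.5.5 and Appendix 5 was found.

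**How different the two actions are.** Section 6 defines a month as 30 days, so recovery in 1-2 months is about 30-60 days. That exceeds the 14-day limit in Appendix 4: "The treatment lasted for 4 weeks or more and was interrupted for more than 14 consecutive days". For most treated patients, interruption until recovery therefore also means a monitored restart.

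**What the database would show.**
- Part One: scheduled counts are central-laboratory data sent electronically for the database (Sections 6.5.4 and 8.3), and notable values trigger a phone alert to the investigator. Appendix 5 lets monthly repeats be done locally, with an eCRF comment, so these too leave a trace.
- Part Two, count judged clinically significant: reported as an adverse event (Table 6-2, footnote 7), with the action taken on the Adverse Event eCRF (Section 7.1).
- Part Two, drug interrupted: recorded on the Dosage Administration Record (Section 5.5.5). If the drug is restarted, the date and reason are documented as well (Section 5.5.9).
- Part Two, confirmed low count neither judged clinically significant nor acted on: visible only in source documents.

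Only the last case is hidden from the database.

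**The case against.** The strongest reply is that the texts fit together. Section 5.5.5 is conditional on confirmation. Appendix 5 starts at the first low value, asks for repeats and permits a pause meanwhile. A site can do both, and nothing in Appendix 5 forbids what Section 5.5.5 directs. Appendix 5 also plainly contemplates interruption, since it describes recovery after stopping. This stands as far as it goes: the conflict is between a directed and a discretionary action, not between a mandate and a prohibition. It does not remove the point, because neither text states the sequence and discretion is the only interruption rule Appendix 5 gives.

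A reader might infer that Section 5.5.9 also makes Appendix 5 the governing text, because it says "study drug must be discontinued based on results of safety monitoring as outlined in" that appendix. The documents do not support this. The Glossary defines study drug discontinuation as permanent, whereas the lymphopenia rule concerns a temporary pause. For that action only Section 5.5.5 sends sites to Appendix 5.

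A reader might also infer that departures from Section 5.5.5 would generally go unseen, or that patients are exposed to more infections. The recording rules set out above confine the first to one narrow Part Two case. On the second, Section 1.1 reports no clear relationship between lymphocyte count and infections. Safeguards also apply under either reading:
- Section 5.5.9 requires stopping when the investigator sees significant risk.
- Counts are repeated at least monthly, with counselling.
- For infections, Appendix 5 adds: "Investigators are requested to specifically ask about infections at each visit".

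**Conclusion.** The inconsistency is real and minor. One threshold carries two instructions, and they diverge only for a confirmed count below 0.2 x 10^9/L. There, a site following Appendix 5 alone could continue the drug where Section 5.5.5 directs interruption.

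The size cannot be put in patients, because the documents do not give the number with a confirmed count that low. No effect on infections is claimed. No analysis in either SAP uses the interruption rule, so no study-level result is in question. The conclusion rests on the current text of both places and on the absence of any statement of precedence. If the sponsor intended the sequential reading, the gap is a missing link between two compatible rules. If it intended discretion throughout, Section 5.5.5 is the text that needs changing.

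**What to change.** Leave Section 5.5.5 unchanged. In the Appendix 5 lymphopenia guidance, replace the discretion sentence with:

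> Before confirmation, interruption is at the investigator's discretion; if a repeat count confirms <0.2 x 10^9/L, study drug should be interrupted until recovery (see Section 5.5.5).

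This keeps the more protective rule. It does not say how soon a confirming repeat must be taken or what count marks recovery, so sites could still differ on timing. Both are optional clarifications for the sponsor's clinical team.

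The procedural cost follows from Section 11.1: "Any change or addition to the protocol can only be made in a written protocol amendment". Approval is needed from the sponsor, the IRB/IEC and, where required, Health Authorities, in a study planned for more than 500 centers. That is too much for this sentence alone, so it should be bundled with the next amendment. The clinical cost is possibly a few more interruptions, with first-dose monitoring at restart when they run past 14 days in patients treated for 4 weeks or more. No new assessments are needed.
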